-Slit-lamp biomicroscopic examination of the anterior segment structures: eyelid margins, conjunctiva, sclera, cornea, anterior chamber, iris, lens, and anterior vitreous

-Intraocular pressure (IOP) measurement

-Following dilation of the pupil, continued slit-lamp biomicroscopic examination of anterior segment structures with clinical grading of lens opacity

-Fundus slit-lamp biomicroscopic examination, including use of accessory diagnostic lenses, to view the vitreous, retina, macula, vasculature, and optic nerve

4-if changes on exam or ancillary testing are noted, fundus photography and autofluorescence should be utilized if clinically indicated.

Footnotes (a-e)

- **a-** Within 56 days of starting therapy
- **b-** +/- 1 week to allow for scheduling difficulties
- c- +/- 2 weeks to allow for scheduling difficulties
- d- After 2 years patients will continue to be followed every six cycles (months). At the half-year follow-ups (e.g. 2.5 y, 3.5 y, etc), exams will comprise the same components as the 1.5 y exam. At the annual follow-ups (e.g. 3y, 4y, etc), the exam will comprise the same components as the 2 year exam.
- e- If end of study occurs within 3 cycles (months) of the most recent scheduled exam, no additional testing is required unless ophthalmic concerns played a role in discontinuation in which case a full end of study exam is conducted. If end of study falls outside of this timeframe, the end of study eye exam should be captured when feasible.

CTCAE Grade ^a	Adverse Event Management	Action and Dose Modification
Grade 1 ^b	 Consult ophthalmologist within 7 days of onset 	 If dilated fundus examination cannot be performed within 7 days of onset, interrupt binimetinib and hydroxychloroquine until RVO, and visual field deficit can be excluded by retina specialist/ophthalmologist.
		 If and RVO excluded, continue (or restart) binimetinib and HCQ at same dose level
		If RVO diagnosed: Permanently discontinue binimetinib and report as SAE.
Grade 2 and Grade 3	 Consult ophthalmologist immediately Interrupt binimetinib and HCQ. 	 If RVO excluded, restart binimetinib and HCQ at same dose level.
		If RVO diagnosed: Permanently discontinue binimetinib and report as SAE
Grade 4	Consult ophthalmologist immediatelyInterrupt binimetinib and HCQ.	• If visual field deficit and RVO excluded, may consider restarting binimetinib at same or reduced dose after discussion with study medical monitor

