		 If RVO or visual field deficit diagnosed, permanently discontinue binimetinib and report as SAE.

Table 4 Management and Dose Modification Guidelines for Visual Changes and/or Ophthalmic Examination Findings

Abbreviations: RPED = retinal pigment epithelial detachment; CTCAE = Common Terminology Criteria for Adverse Events; RVO= retinal vein occlusion; SAE = serious adverse event

- a. Refers to CTCAE Version 5.0 'Eye disorders Other, specify'
- b. If visual changes are clearly unrelated to study treatment (e.g., allergic conjunctivitis), monitor closely but ophthalmic examination is not required.

Table 5 Recommended dose modifications for binimetinib for retinal pigment epithelial detachments (RPED)

CTCAE Grade	A	ction and Dose Modification
Grade 1 RPED (Asymptomatic; clinical or diagnostic observations only)	•	Continue treatment with retinal evaluation each cycle (monthly) until resolution. If RPED worsens follow instructions below
Grade 2-3 RPED (Symptomatic with	•	Interrupt binimetinib and hydroxychloroquine
mild to moderate	•	Retinal evaluation each cycle (monthly)
decrease in visual acuity; limiting instrumental ADL)	•	If improved to ≤ Grade 1, restart binimetinib at lower dose or discontinue in patients taking lowest dose

Table 6 Management of Ocular Toxicities

Ocular Toxicity	Uveitis, conjunctivitis	Retinal Vein occlusion, retinal pigment epithelial detachment (RPED), papilledema.	Visual field deficits
Action	Continue all therapies as long as effective local therapies can control inflammation	See table 3, 4, 5	Discontinue HCQ

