5.3.2 Hydroxychloroquine Dose Reduction

Any AE of \geq Grade 3 and attributed as possibly, probably or definitely related solely to HCQ will result in the dose being held until the AE has resolved to \leq grade 1 or baseline while binimetinib dosing may continue uninterrupted. If the AE resolves, reinstitution of treatment can occur but at a reduced dose as described in Table 5. If the AE recurs at the reduced dose, treatment will be held until the AE has resolved to \leq grade 1 and when resolved treatment can be reinstituted at the next lower dose level. No more than 2 dose reductions are allowed during the maintenance cycles.

Toxicities that may be attributable to HCQ include: nausea, anorexia, vomiting, constipation, diarrhea, rash, and visual field deficit. If any of these AEs occur at grade ≤ 2 , HCQ may be continued and the AE managed with supportive care. For any AE with a grade ≥ 3 , HCQ dose will be held until the toxicity resolves to \leq grade 2, after which HCQ may be restarted at a reduced dose as described in table 5. With particular regard to visual field deficits patients should be cautioned to report any visual symptoms, particularly difficulty seeing entire words or faces, intolerance to glare, decreased night vision, or loss of peripheral vision. These symptoms of retinal toxicity or subclinical evidence of retinal toxicity on scheduled eye exams should prompt drug discontinuation and ophthalmologic evaluation.

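### After a grade 2–3 visual field deficit the protocol both restarts hydroxychloroquine at full dose (Table 4) and stops it (Table 6)

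*Combined protocol and SAP*

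**What the plan says.** Four places in the protocol tell the clinician what to do with HCQ when a visual field deficit appears and RVO has been excluded.

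- **Section 5.3.2, general sentences.** Visual field deficit is on the list of toxicities that may be due to HCQ. For anything on that list at grade 2 or below, "HCQ may be continued and the AE managed with supportive care". At grade 3 or above HCQ is held, "after which HCQ may be restarted at a reduced dose as described in table 5". The table cited is headed "Table 5 Recommended dose modifications for binimetinib for retinal pigment epithelial detachments (RPED".
- **Section 5.3.1, Table 4, grades 2 and 3.** Both drugs are interrupted and an ophthalmologist is consulted at once. Then: "If RVO excluded, restart binimetinib and HCQ at same dose level". The row does not mention field deficit. The table's title is "Table 4 Management and Dose Modification Guidelines for Visual Changes and/or Ophthalmic Examination Findings".
- **Section 5.3.1, Table 6, visual field deficits column.** "Discontinue HCQ", with no grade limit.
- **Section 5.3.2, closing sentence.** Following a remark directed specifically at field deficits: "These symptoms of retinal toxicity or subclinical evidence of retinal toxicity on scheduled eye exams should prompt drug discontinuation and ophthalmologic evaluation".

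The grade 4 row of Table 4 treats field deficit as a separate condition: "If visual field deficit and RVO excluded, may consider restarting binimetinib at same or reduced dose after discussion with study medical monitor". That row interrupts HCQ and offers no HCQ restart.

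**The concern.** A clinician with one patient and one diagnosis can find a passage that supports continuing, reducing, restarting at full dose or stopping HCQ. Section 2.4 names retinopathy as the characteristic cumulative toxicity of chloroquine (while giving HCQ a wider therapeutic index), and the end of 5.3.2 treats even subclinical retinal findings as a reason to stop. Following the grade 2–3 row of Table 4 to the letter therefore re-exposes a patient with possible retinal toxicity to the suspect drug. Section 7.2.1 gives mean elimination half-lives of 30 to 50 days in its account of HCQ and its metabolites, so exposure from a mistaken restart would not clear quickly.

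There is also a cost to the data. Safety is a primary objective (1.1), and 5.3.1 says the ocular findings will be summarised to characterise the risk of the combination. If similar events are handled under different rules, that summary is harder to interpret.

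**Working it through.** The plan has no figure to reproduce here; the check sets the passages side by side and then sizes one case.

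**Inputs.** HCQ is given at 400 mg twice daily in 28-day cycles (4.1), so 400 × 2 = 800 mg/day. Table 1, the only dose-level table, covers binimetinib alone (45, 30 and 15 mg twice daily). Section 4.2 gives HCQ a starting dose and no lower level. Table 5 contains binimetinib actions for RPED and no HCQ dose. Table 3 schedules 10-2 visual fields at baseline and cycles 7, 13, 19 and 25.

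**HCQ dose for a field deficit with RVO excluded**

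| Passage followed | Grade 2 | Grade 3 |
|---|---|---|
| 5.3.2, general sentences | 800 mg/day, no interruption required | Hold, then a reduced dose that is nowhere defined |
| Table 4, grades 2 and 3 | Interrupt, then 800 mg/day | Interrupt, then 800 mg/day |
| Table 6 | 0 | 0 |
| 5.3.2, closing sentence | 0 | 0 |

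At each grade the instructions cannot all be followed.

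**Is field deficit within Table 4's scope?** Yes. The title covers visual changes and examination findings in general. The grade 1 row, when the fundus examination is delayed beyond 7 days, holds both drugs until RVO and field deficit are both ruled out. The grade 4 row also requires both to be excluded before binimetinib is reconsidered. Only the grade 2–3 row drops field deficit. So a grade 1 event with a delayed examination faces a stricter test than a grade 2 or 3 event.

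**Rows that are incomplete but not contradictory.** The grade 1 restart condition appears to be missing a term; this may come from text extraction and carries no weight here. The grade 4 row is compatible with Table 6 but does not say that HCQ stops when a field deficit is diagnosed.

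**Size of the dose difference, one illustration.** Suppose the deficit is found at the cycle 7 field test and HCQ is restarted under Table 4. The next scheduled 10-2 test is at cycle 13:

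- Interval at nominal dates: (13 − 7) × 28 = 168 days.
- HCQ taken: 168 × 800 mg = 134,400 mg = 134.4 g, against 0 g under Table 6.

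This assumes full dosing with no time off. If footnote 4 of the study calendar (section 8) is read as requiring an eye examination every 12 weeks beyond cycle 8, a 12-week (84-day) interval gives 84 × 800 mg = 67.2 g. Unscheduled examinations (Table 3, footnote 2) could shorten either interval.

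**The case against.** The best defence is that the protocol's structure already makes stopping the governing rule.

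- Section 5.3 opens by separating listed toxicities, which have specific guidance, from unlisted ones, which go to general guidance said to be in Table 5. Field deficit is listed, with its own column in Table 6.
- Table 6 sends RVO, RPED and papilledema to Tables 3 to 5 but gives field deficit its own action. Table 4, graded on the CTCAE category for other eye disorders, can then be read as a work-up table for undiagnosed visual change.
- Within 5.3.2, a permissive general sentence is followed by a firmer one aimed at field deficits, which is ordinary rule-then-exception drafting.
- The header of Table 2 excludes retina disorders from discretionary HCQ continuation, and the note after that table urges caution.

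It can also be said that the 134.4 g figure stacks unfavourable assumptions, that every comprehensive eye examination includes confrontation fields, and that section 2.4.1 reports no significant ocular toxicity on serial examinations with dabrafenib, trametinib and HCQ.

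Much of this stands. Stopping is the likely intent, and the gram figure is an illustration, not an estimate. The missing HCQ dose levels also affect every HCQ toxicity of grade 3 or above and are a wider problem.

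The conflict remains all the same. Table 4 is as specific to the eye as Table 6, and it names field deficit in the rows on either side of the one at issue. Section 5.3.2 puts field deficit on its own general list. The Table 5 named in the opening of 5.3 holds no general guidance. No sentence ranks Table 4 against Table 6.

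**Conclusion.** The point holds: the rule is wrong as written. For a grade 2–3 visual field deficit without RVO, the protocol supports 800 mg/day, an undefined lower dose (grade 3), or no HCQ, and sets no order of precedence. This rests on the wording of 5.3.2 and Tables 1, 4, 5 and 6 and does not depend on the gram figures.

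It should be fixed, but its reach is limited. It concerns only patients who develop a field deficit, among at most 29 enrolled, and the protocol gives no incidence. Immediate ophthalmology consultation, interruption of both drugs in Table 4, and referral of ophthalmic concerns to the medical monitor (10.6) all lower the risk. None of them says which HCQ dose applies, and the grade 2–3 row, unlike grade 4, does not require discussion with the monitor before restart. The Simon design figures are unaffected.

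**What to change.** Keep the Table 6 rule and bring the other passages into line with it.

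1. **Section 5.3.2.** Take visual field deficit out of the list governed by the grade 2-or-below sentence and refer to Table 6 instead. Add *except visual field deficit (see Table 6)* to both sentences for grade 3 or above. Both apply to any adverse event, so editing the list alone would leave the grade 3 conflict in place.
2. **Table 4, grades 2 and 3.** Allow both drugs to restart at the same dose only when RVO and visual field deficit are both excluded. Add: *Visual field deficit diagnosed: stop HCQ (Table 6); binimetinib may restart at the same dose if RVO is excluded.* This leaves that row's binimetinib rule unchanged.
3. **Table 4, grades 1 and 4.** Complete the grade 1 restart condition in the same way. In grade 4, state that HCQ stops when a field deficit is diagnosed.

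The reference to Table 5 for reduced HCQ doses still needs separate correction for other toxicities, because no HCQ dose levels are defined.

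The cost is wording in 5.3.2 and Table 4 within one amendment, with its review time. Table 6 is unchanged and no examinations are added. The clinical downside is that some patients with a mild field deficit, who could have continued under the general sentence, will stop HCQ; Table 6 already prescribes that.

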6.0 PHARMACEUTICAL INFORMATION

Array BioPharma Inc. is providing Binimetinib (Mektovi®) in order to conduct this study. Hydroxychloroquine is commercially available.

Drug accountability logs and pharmacy records must be maintained at each pharmacy location and must be available for review upon request. Drug accountability logs and pharmacy records will be reviewed during monitoring visits, and by the ACC Department of Compliance and Monitoring (DOCM) at the time of each audit.

For complete information please refer to the package inserts at http://dailymed.nlm.nih.gov/dailymed/

6.1 Hydroxychloroquine

Generic name:	Hydroxychloroquine sulfate
Commercial name:	Plaquenil
Chemical name:	7-Chloro-4-[4-[ethyl-(2-hydroxyethyl)amino]-1-methylbutylamino] quinolone
Source:	Commercially available

6.2 Binimetir	nib						
Generic name	e:	Binimetinib					
Commercial r	name:	Mektovi					
Chemical nar	ne:	5-[(4-bromo-2-fluorophenyl)amino]-4-fluoro-N-(2 hydroxyethoxy)-1- methyl-1H-benzimidazole-6-carboxamide					
Source:	Study	provided (see the Manual of Procedures for ordering instructions)					

Storage and Handling: Binimetinib film-coated tablets are packaged in plastic bottles or in blister packs acceptable for pharmaceutical use.

- Binimetinib film-coated tablets packaged in plastic bottles should not be stored above 25 degrees Centigrade and should be protected from the light
- Binimetinib film-coated tablets packaged in opaque polyvinyl chloride (PVC)/polyvinylidene chloride (PVDC) blister packs do not require any specific storage conditions

Binimetinib oral suspension prepared from 15 mg binimetinib tablets should not be stored above 25 degrees Centigrade and should not be refrigerated. The constituted suspension should be used within 30 days after preparation.

7.0 CORRELATIVE STUDIES

7.1 Overview of Correlative Studies.

A number of blood and tissue collections are involved in this study to address important research questions. For patients with safely biopsiable disease, a biopsy may be performed prior to study enrollment and again after 3 weeks of therapy. This biopsy is encouraged, but optional. We aim to have 5 patients undergo biopsy. We will also collect plasma at each visit for autophagy biomarkers, whole blood for HCQ PK, and archival tumor tissue will be collected for all patients.

Summary of timing for correlative study collections:

- I. HCQ PK: Pre-treatment (baseline and/or C1D1 prior to therapy), during combination therapy: at every cycle (monthly) visit
- II. Biopsy (Optional) at
 - 1) Baseline
 - 2) C1D21 ± 7 days
- III. Plasma for autophagy dynamics (All enrolled subjects):
 - 1) Pre-treatment (baseline and/or C1D1 prior to therapy)
 - 2) D1 of each cycle for C1-4
 - 3) Sample obtained at progression
- IV. Archival tissue (All enrolled subjects)

Obtain 20 unstained slides from archival FFPE blocks

Table 7 Blood collection schedule

Sample	Pre-treatment	C1D1*	C2D1	C3D1	C4D1	CXD1
Туре						
Plasma	Х	Х	Х	Х	Х	
HCQ PK	Х	Х	Х	Х	Х	Х

*At least one collection pre-treatment is required prior to C1D1 treatment, both time points are encouraged

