7.2.2 Pharmacokinetic Sample Collections

A sparse sampling approach will be applied to all patients that consists of blood collection pretreatment, and monthly after start of B+HCQ. A 5 mL venous blood sample for determination of HCQ in anticoagulated whole blood will be collected in a heparinized green-top tube and placed on ice until it can be aliquotted into three polypropylene tube and stored at -80°C. Centrifugation is not required. All specimens will be labeled with the patient's assigned study number, day on study, date and time. A separate log of patient samples will also record this information, and in addition, the time of last HCQ and last binimetinib dose, and time of last meal, and a description of concomitant medications at the time of collection. The PK blood draw should be scheduled for the convenience of the subject. For these sparse sampling collections, patients will be asked to continue their drug dosing as scheduled and not hold any doses even on days of blood draws. For HCQ, one sample will be collected during each visit for the first year that will also ensure random collections at times both pre- and post-HCQ dose. The time of last administration of HCQ and the time of the blood draw should be recorded.

7.2.3 Bioanalytic Methods and PK analysis.

The bioanalytic method and pharmacokinetic analysis will be performed at the University of Arizona under the aegis of [name].

Hydroxychloroquine. Whole blood concentrations of HCQ and its metabolites (DHCQ, DCQ, BDCQ) will be measured using a modification of published high-performance liquid chromatography methods using fluorescence and tandem mass spectrometry detection (HPLC-MS/MS). CQ will be used as the internal standard. Briefly, the blood will be alkalinized and then subjected to ether extraction to extract HCQ and its metabolites. The ether extracts will be

evaporated to dryness and reconstituted in mobile phase. A methanol-based mobile phase will be used to separate the analytes. Elution of the analytes will be analyzed simultaneously using fluorescence and mass detection with a Varian LC 1200 triple quadrupole mass spectrometer. Whole blood concentrations of HCQ will be calculated for each sample based on a standard curve of peak area ratios of the drug and internal standard (CQ).

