11.5 Plans for Data Analysis

Primary

- The objective response rate and 95% exact confidence interval will be calculated.
- All observed toxicities will be graded and tabled (worse grade experienced in all cycles). The
 overall rate of > grade 3 toxicity and 95% exact confidence interval will be calculated.

Secondary

• Progression-free survival and overall survival will be estimated by the method of Kaplan and Meier. Median values and 95% confidence intervals will be calculated.

Exploratory

- Associations between objective response and expression of biomarkers pre-treatment will be tested using nonparametric Wilcoxon rank sum test. Comparisons of pre- and post-treatment biomarker expression will be conducted using Wilcoxon signed ranks test for paired data.
- Describe autophagic vesicles/cell in tumor tissue at various time points using descriptive statistics and scatter plots.
- To evaluate HCQ pharmacokinetics and pharmacodynamics to determine whether changes in blood-based autophagy biomarkers (ctDNA KRAS allelic frequency) reflect tissue-based changes in autophagy (autophagic vesicles/cell), the nonlinear mixed–effects modeling approach (NONMEM) will be used to perform a full population PK analysis. PK-PD analyses to be conducted by University of Sciences of Philadelphia. Analysis methods – See Section 18. The key variables for the population include the Cmax and half life. Population PK will be assessed and qualitatively compared to population PK findings from other HCQ studies. No hypothesis testing will be performed for any of the vairables.

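### HCQ half-life is named a key PK variable, yet no HCQ sample is scheduled after the last dose; one tube at the existing 30-day safety visit would inform it directly

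*Combined protocol and SAP*

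**What the plan says.** **Early draws.** Section 7.1 gives the HCQ PK schedule as "Pre-treatment (baseline and/or C1D1 prior to therapy), during combination therapy: at every cycle (monthly) visit". The Table 7 note adds "At least one collection pre-treatment is required prior to C1D1 treatment, both time points are encouraged". Section 7.2.2 describes "blood collection pretreatment, and monthly after start of B+HCQ". The first scheduled on-drug sample is therefore C2D1, about day 29.

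**Later draws.** Section 7.2.2 states "The PK blood draw should be scheduled for the convenience of the subject" and also "one sample will be collected during each visit for the first year that will also ensure random collections at times both pre- and post-HCQ dose". Dosing is not interrupted for sampling: "patients will be asked to continue their drug dosing as scheduled and not hold any doses even on days of blood draws". Times are captured: "The time of last administration of HCQ and the time of the blood draw should be recorded".

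**After the last dose.** Table 7 ends with the day-1 draw of later cycles. In the section 8 calendar, the research blood row is marked at the end-of-treatment visit, which takes place at discontinuation. It is blank at the safety follow-up visit 30 days later, where CBC and serum chemistry are marked.

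**Targets.** Section 11.5 states "The key variables for the population include the Cmax and half life". Section 7.2.3 lists only CL/F and Vd/F as estimated population parameters, and takes Cmax and Cmin from model predictions. Section 11.5 places this work under exploratory analyses, with a qualitative comparison against other HCQ studies and no hypothesis tests.

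**The concern.** A half-life is learned either from the approach to steady state or from the decline after dosing stops. The plan schedules only the first kind of sample. Section 7.2.1 itself says that late-phase samples matter for steady-state parameters, and those come only from patients who stay on treatment. The documents do not say how long patients are expected to stay.

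At stake is the comparison of HCQ PK in this combination with earlier HCQ data. Sections 7.2.1 and 7.2.3 want it as a signal of a drug interaction, and a marked difference could lead to a fuller interaction study. Binimetinib PK is not measured, so the HCQ data carry that question alone. A sample not taken cannot be recovered later.

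**Working it through.** The plan gives no precision figure for the PK analysis, so there is none to reproduce.

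**1. Inputs from the documents.** 28-day cycles (4.1); HCQ 400 mg every 12 hours (4.1, 4.2); 10 to 29 patients (11.6); safety visit 30 days after end of treatment (8.0); half-life T of 30-50 days (7.2.1). Section 7.2.1 attributes that range to the metabolites, so using it for HCQ is an assumption.

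Ten patients is a realistic case. At a true ORR of 10%, the chance of stopping after stage 1 is 0.9^10 + 10 × 0.1 × 0.9^9 = 0.349 + 0.387 = 0.736, which agrees with the 0.74 in section 11.4.

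**2. Where the half-life information lies.** Fraction of steady state at day t is 1 − 2^(−t/T). Fraction remaining 30 days after the last dose is 2^(−30/T).

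| T (days) | day 28 | day 56 | day 84 | day 168 | left after 30 days |
|---|---|---|---|---|---|
| 30 | 48% | 73% | 86% | 98% | 50% |
| 40 | 38% | 62% | 77% | 95% | 59% |
| 50 | 32% | 54% | 69% | 90% | 66% |

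- Two on-drug draws: the day 56 to day 28 ratio is 1 + 2^(−28/T), which is 1.52 at T = 30 and 1.68 at T = 50. The whole range of T moves it by 1.68/1.52 = 1.10.
- Six on-drug draws: the day 168 to day 28 ratio is 2.06 at T = 30 and 2.81 at T = 50, a factor of 1.36.
- One sample 30 days after stopping: 0.66/0.50 = 1.32, however many cycles came before.

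Accumulation therefore informs half-life in patients who stay and says little in those who leave after two cycles. The post-treatment sample fills that gap.

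**3. Precision.** One-compartment oral model with log-normal CL/F and V/F, and half-life = ln 2 × (V/F)/(CL/F). For each patient, J holds the derivatives of log concentration with respect to log CL/F and log V/F. The information is the sum over patients of J′(JΩJ′ + σ²I)⁻¹J, and Var(log T) = g′F⁻¹g with g = (−1, 1).

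Assumptions not in the documents: CL/F 15 L/h; absorption rate ka fixed at 0.7/h; between-patient SD 0.45; residual SD 0.25; draws 3 h after a dose; exponential time on treatment with a median of 3 cycles; every patient has at least one on-drug draw and attends the 30-day visit. Relative standard error (RSE) of half-life over T = 30-50 days:

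| Design | N = 29 | N = 10 |
|---|---|---|
| As planned | 18-19% | 31-32% |
| Plus 30-day sample | 13-15% | 23-25% |

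The two columns differ by √(29/10) = 1.70, as they should.

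**4. Dependence on time on treatment.** A second assumption set: T = 40 days, between-patient CV 35%, residual error 30%, ka 0.3/h, draws 0-8 h after a dose. RSE of half-life, planned → with the 30-day sample:

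| Cycles on treatment | N = 29, ka fixed | N = 10, ka fixed | N = 29, ka estimated |
|---|---|---|---|
| all 2 | 44% → 14% | 74% → 24% | 92% → 38% |
| mixed, 2 to 12 | 20% → 13% | 34% → 22% | 27% → 23% |
| all 6 | 14% → 11% | 24% → 19% | 21% → 18% |

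**5. Cmax and draw timing.** With CL/F 15 L/h, V/F = 15 × 24 × T/ln 2, about 15,600 L at T = 30 and 26,000 L at T = 50. One 400 mg dose adds 400/V = 0.026 to 0.015 mg/L to a steady-state average of 400/(15 × 12) = 2.2 mg/L, or 1.2% to 0.7%. In this model, the time since the last dose hardly moves an on-treatment concentration. Under the second assumption set with mixed cycles, model-predicted Cmax has an RSE of about 10% at N = 29 and 17-18% at N = 10.

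**The case against.** The strongest reply is that sparse sampling is a deliberate choice, argued for in section 7.2.1, and that an RSE near 20% is acceptable for exploratory PK with a qualitative comparison. That stands, and it limits the weight of the point.

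Second, section 7.2.3 builds the population model on a wider group, including patients given HCQ with other agents, and uses it as prior information. Precision could then be better than calculated here. But the more the half-life is borrowed from other HCQ data, the less it can serve as a comparison with those data.

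Third, the section 7.2.2 wording on sampling at each visit in the first year could be stretched to cover the safety visit. Table 7 and the calendar do not support that, since neither marks it.

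Fourth, the parameter values are assumptions. The gain from the 30-day sample alone is smaller if ka must also be estimated (27% → 23% with mixed cycles, N = 29), and smaller still if patients miss the visit.

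Some stronger readings are tempting but not supported:

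- *Half-life cannot be estimated without washout.* It can, from accumulation, when patients stay several cycles.
- *Cmax is poorly informed.* Section 7.2.3 makes Cmax a model prediction, and its precision is reasonable with mixed cycles. The planned draws cannot identify the absorption rate (RSE above 1000%), so a peak distinct from the average level would rest on a fixed value. That is narrower than saying Cmax is poorly informed.
- *Convenience timing spoils the data, so draws need assigned pre- and post-dose windows.* Dose and draw times are recorded, and in this model timing moves the level by about 1%.
- *Both early draws read zero.* Prior HCQ use is not excluded, and the Table 7 note requires only one pre-dose draw.

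**Conclusion.** The point holds as a low-priority improvement. The plan names half-life as key and schedules no HCQ sample that observes elimination. Under the stated assumptions, a sample at the 30-day visit lowers the RSE of half-life by about 4 to 5 percentage points at N = 29, and by about 7 to 8 at N = 10. The benefit is largest when patients stop early (44% → 14% if all stop after 2 cycles, N = 29, ka fixed). It is small if most reach 6 cycles (14% → 11%).

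The absolute figures rest on a one-compartment model, on a half-life range quoted for the metabolites, on assumed variability and on full attendance at the 30-day visit. The absence of a scheduled post-treatment sample, and the value of one when time on treatment is short, do not depend on the exact values. Nothing here affects the ORR or safety analyses.

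**What to change.** In Table 7, section 7.2.2 and the section 8 calendar, add one 5 mL HCQ PK tube to the bloods already taken at the 30-day safety visit, and record the dates and times of the last HCQ dose and of the draw. The cost is one extra tube and one assay per patient at an existing venepuncture, plus the matching wording in the laboratory manual.

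Optional: where a baseline blank already exists, take the C1D1 HCQ sample a few hours after the first dose in place of a second blank. This informs absorption and central volume. Its value for half-life depends on the model: under the section 3 assumptions it gives 15-16% alone at N = 29, and 13-14% together with the 30-day sample. It may need a second venepuncture, because the C1D1 plasma sample in section 7.1 is also taken before therapy.

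No change to the timing of the other monthly draws is needed.
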